7.2.2 Research Assays

The volume of venous blood to be collected for immunogenicity assays and future research is presented in **Appendix A**.

Immunogenicity

Assays to determine serum levels of hepatitis E antibodies (IgG and IgM) will be performed at Emory's VTEU laboratory. Venous blood samples (approximately 10 mL) for antibody assays will be collected from each subject at screening and sent directly to Emory's VTEU laboratory for baseline testing. Seronegative samples will be defined as per the Wantai HEV-IgM and IgG ELISA package inserts (A/C.O. <0.9).

Venous blood samples (approximately 10 mL) will be collected immediately prior to each study vaccination (Days 1, 29, and 180) and Days 8, 15, after each study vaccination (Days 8, 15, 36, 43, 187, 194), Day 29 after each boost vaccination (Days 57 and 208), and Day 360. Subjects who withdraw early will have hepatitis E antibody assays run on available sera. Samples for immunogenicity assessments will be shipped from the DMID CMS to Emory's VTEU laboratory for vaccine immunogenicity assessments beginning with the completion of the Day 360 visit.

Seroconversion will be defined as a change from a seronegative result to a seropositive result as defined by the Wantai HEV-IgM and IgG ELISA package inserts (A/C.O. >1.1). As defined by

DMID/NIAID/NIH

DMID Protocol 15-0108	Version 2.0
Phase I Study of HEV-239	08 FEB 2019

prior studies,²⁴ the antibody concentration in samples negative for hepatitis E virus IgG was set at 0.0385 Wu/mL which was half the lower limit of quantification. A 4-fold seroconversion will be defined as a HEV IgG \geq 0.154 in a subject that was HEV seronegative at Day 1.

Future Use:

Residual samples are those that are left over after the study has been completed and are stored for possible use in future research studies. Future use samples are extra tube(s) of blood collected and stored for possible use in future research studies. Retention of residual and future use samples and the potential for use in future research studies will be a condition of study participation. Subjects who sign the informed consent form for the study are consenting to allow the collection, storage and use of any residual samples (serum or cells derived from venous blood samples) or future use samples for possible use in future research studies, such as examining additional immunological assessments or testing for antibodies against other viruses or bacteria. Future use research studies may include, but are not limited to non-traditional immune assay development, assessing innate immune factors, and the ability of HEV vaccine-induced antibodies to cross-react with other viruses.

Residual and future use samples will be encoded with a barcode label and unique tracking number to protect subject identity. Samples will be stored indefinitely at a DMID designated central storage facility. Residual samples may be shared for purposes other than per protocol analysis with investigators at participating VTEU sites and with investigators at other institutions once the clinical study report has been finalized. Future use research samples may be requested from DMID and shipped from the DMID CMS at any time.

Residual and future use samples will not be sold or used directly for production of any commercial product. Genetic tests may be performed on samples. There are no benefits to subjects in the collection, storage and subsequent use of their specimens for future research. Reports about future research done with subjects' samples will NOT be kept in their health records.

Subjects may withdraw consent for study participation at any time by notifying the study doctors or nurses in writing. However, any data from sample(s) collected prior to the withdrawn consent will not be removed including genomic data. There will be no further use of residual samples or collection and use of future use samples after consent has been withdrawn.

Venous blood will be collected for PBMCs and plasma (16-64 mL) for future use on Days 1, 8, 15, 29, 36, 43, 57, 180, 187, 194, 208, and 360.

DMID/NIAID/NIH

7.2.2.1 Laboratory Specimen Preparation, Handling, and Storage

Instructions for specimen preparation, handling, and storage are included in the central (clinical) laboratory manual and protocol-specific MOP as appropriate.

7.2.2.2 Laboratory Specimen Shipping

Specimen shipment will occur at intervals during the course of this trial following all applicable International Air Transport Association (IATA) requirements and according to the specifics for storage temperature and documentation as detailed in the central (clinical) laboratory manual and protocol-specific MOP as appropriate.

Specimens for safety laboratory evaluation will be shipped from the Emory VTEU to the clinical laboratory.

Screening: Specimens for initial immunogenicity laboratory evaluations at screening will be sent to the Emory VTEU laboratory in an unblinded manner. Results will be conveyed back to the Emory VTEU clinical team.

Enrolled Subjects: Specimens for immunogenicity laboratory evaluations beginning Day 1 and continuing throughout the study will be shipped from the Emory VTEU to the central repository and then provided by the DMID CMS to Emory VTEU laboratory in a blinded manner.

Further instructions for specimen shipment are included in the central (clinical) laboratory manual and protocol-specific MOP, as appropriate.

DMID/NIAID/NIH

CONFIDENTIAL

Phase I Study of HEV-239

8 ASSESSMENT OF SAFETY

Regulatory requirements including the FDA regulations, ICH Guidelines for GCP, and European Union (EU) Clinical Trials Directive set forth safety monitoring and reporting responsibilities of sponsors and investigators to ensure the safety and protection of human subjects participating in clinical trials.

Responsibilities

Investigators participating in this clinical trial are responsible for and will:

- Evaluate subject safety including assessment of AEs for seriousness, severity, and causality;
- Follow up AEs resolution through study follow up period;
- Notify the sponsor (DMID) of SAEs immediately;
- Follow up SAEs until resolution, even if this extends beyond the follow up period (resolution of an AE/SAE is defined as the return to baseline or stabilization of the condition with the expectation that it will remain chronic) provide detailed written reports, including necessary documentation requested by the sponsor or Institutional Review Board(IRB)/Independent Ethics Committee (IEC), promptly following immediate initial reports, and;
- Inform the IRB/IEC of AEs as required by applicable regulatory requirements.

8.1 Assessing and Recording Safety Parameters

8.1.1 Adverse Events (AEs)

ICH E6 defines an AE as any untoward medical occurrence in a patient or clinical investigation subject administered a pharmaceutical product regardless of its causal relationship to the study treatment. FDA defines an AE as any untoward medical occurrence associated with the use of a drug in humans, whether or not considered drug related.

An AE can therefore be any unfavorable and unintended sign (including an abnormal laboratory finding), symptom, or disease temporally associated with the use of medicinal (investigational) product. The occurrence of an AE may come to the attention of study personnel during study

DMID/NIAID/NIH

visits and interviews of a study recipient presenting for medical care, or upon review by a study monitor.

All AEs, including solicited local (injection site) and systemic (subjective and quantitative) reactions, will be captured on the appropriate data collection form and eCRF. Information to be collected for AEs includes event description, date of onset, assessment of severity, relationship to study product and alternate etiology (assessed only by those with the training and authority to make a diagnosis and listed on the Form FDA 1572 as an investigator), date of resolution, seriousness and outcome. AEs occurring during the trial collection and reporting period will be documented appropriately regardless of relationship. AEs will be followed through resolution.

Any medical condition that is present at the time that the subject is screened will be considered as baseline and not reported as an AE. However, if the severity of any pre-existing medical condition increases, it should be recorded as an AE.

8.1.1.1 Adverse Events Grading

All AEs (laboratory and clinical symptoms) will be graded for severity and assessed for relationship to study product (see definitions). AEs characterized as intermittent require documentation of onset and duration of each episode. The start and stop date of each reported AE will be recorded on the appropriate data collection form and eCRF. Changes in the severity of an AE will be documented to allow an assessment of the duration of the event at each level of intensity.

Severity of Event:

AEs will be assessed by the investigator using a protocol-defined grading system (toxicity table included as an appendix). For events not included in the protocol-defined grading system, the following guidelines will be used to quantify severity:

- Mild (Grade 1): Events that are usually transient and may require only minimal or no treatment or therapeutic intervention and generally do not interfere with the subject's usual activities of daily living.
- Moderate (Grade 2): Events that are usually alleviated with additional specific therapeutic intervention. The event interferes with usual activities of daily living, causing discomfort but poses no significant or permanent risk of harm to the research participant.

DMID/NIAID/NIH

• Severe (Grade 3): Events interrupt usual activities of daily living, or significantly affects clinical status, or may require intensive therapeutic intervention. Severe events are usually incapacitating.

Relationship to Study Product: The assessment of the AE's relationship to study product will be done by the licensed study physician indicated on the Form FDA 1572 and the assessment will be part of the documentation process. Whether the AE is related or not, is not a factor in determining what is or is not reported in this trial. If there is any doubt as to whether a clinical observation is an AE, the event should be reported.

In a clinical trial, the study product must always be suspect. The relationship to study product will be assessed for AEs using the terms related or not related:

- Related There is a reasonable possibility that the study product caused the AE. Reasonable possibility means that there is evidence to suggest a causal relationship between the study product and the AE.
- Not Related There is not a reasonable possibility that the administration of the study product caused the event.

8.1.2 Reactogenicity (Solicited Local and Systemic Events)

Reactogenicity events are AEs that are common and known to occur following administration of this type of study vaccine. The subject will be instructed on noting the presence and severity of symptoms through D8 after administration of study vaccine: The following Toxicity Grading Scales will be used to grade solicited local (injection site) and systemic (subjective and quantitative) reactions:

Local (Injection Site) Reaction	Mild (Grade 1)	Moderate (Grade 2)	Severe (Grade 3)
Pain – experienced without touching the injection site (spontaneous discomfort)	No pain medication or it requires use of a non- narcotic pain reliever ≤24hours OR does not interfere with activity	Repeated use of non- narcotic pain reliever >24 hours OR interferes with activity	Any use of narcotic pain reliever OR prevents daily activity
Tenderness – hurts only when injection site is	Discomfort only to touch	Discomfort with movement	Significant discomfort at rest

Table 3: Local (Injection Site) Reactogenicity Grading

DMID/NIAID/NIH

Local (Injection Site) Reaction	Mild (Grade 1)	Moderate (Grade 2)	Severe (Grade 3)
touched or the arm is moved			
Pruritus (Itching)	Does not interfere with daily activity	Interferes with daily activity	Prevents daily activity
Ecchymosis (Bruising)*	Does not interfere with daily activity	Interferes with daily activity	Prevents daily activity
Induration (Hardness)/Swelling*	Does not interfere with daily activity	Interferes with daily activity	Prevents daily activity

* Will also be measured in mm but size will not be used as halting criteria.

Erythema (redness), ecchymosis, and induration (hardness)/swelling as analyzed by measurement will be graded as follows:

 Table 4: Local (Injection Site) Reactogenicity Measurements

Local (Injection Site) Reaction	Mild (Grade 1)	Moderate (Grade 2)	Severe (Grade 3)
Ecchymosis (Bruising)*	25mm – 50mm	51 mm – 100mm	>100 mm
Erythema (Redness)*	25 mm – 50 mm	51 mm – 100 mm	>100 mm
Induration (Hardness)/Swelling*	25 mm – 50 mm	51 mm – 100 mm OR interferes with activity	>100 mm OR prevents daily activity

*Will not be used as halting criteria.

Note: Ecchymosis and Induration/Swelling should be evaluated and graded using the symptom scale as well as the actual measurement.

Table 5: Subjective Systemic Reactogenicity Grading

Systemic (Subjective)	Mild (Grade 1)	Moderate (Grade 2)	Severe (Grade 3)
Feverishness (Chills/Shivering/Sweating)	No interference with daily activity	Some interference with daily activity	Significant interference, prevents daily activity

DMID/NIAID/NIH

Systemic (Subjective)	Mild (Grade 1)	Moderate (Grade 2)	Severe (Grade 3)
Fatigue (Tiredness)	No interference with daily activity	Some interference with daily activity	Significant interference, prevents daily activity
Malaise (General Unwell Feeling)	No interference with daily activity	Some interference with daily activity	Significant interference, prevents daily activity
Myalgia (Body Aches/Muscular Pain)*	No interference with daily activity	Some interference with daily activity	Significant interference, prevents daily activity
Arthralgia (Joint Pain)*	No interference with daily activity	Some interference with daily activity	Significant interference, prevents daily activity
Headache	No interference with daily activity	Repeated use of non- narcotic pain reliever >24 hours OR some interference with activity	Significant; any use of narcotic pain reliever OR prevents daily activity OR requires triptans
Nausea	No interference with daily activity	Some interference with daily activity	Significant interference, prevents daily activity
Vomiting	No interference with activity or 1-2 episodes/24 hours	Some interference with activity or >2 episodes/24 hours	Prevents daily activity or requires IV hydration

* Not at injection site.

Oral temperature[#] will be graded as follows:

Table 6: Quantitative Systemic Reactogenicity Grading

Systemic (Quantitative)	Mild (Grade 1)	Moderate (Grade 2)	Severe (Grade 3)
Fever* - oral†	$38.0^{\circ}C - 38.4^{\circ}C$	38.5°C – 38.9°C	>38.9°C
rever - orar	$100.4^\circ F - 101.1^\circ F$	$101.2^{\circ}F - 102.0^{\circ}F$	>102.0°F

[#] Oral temperature assessed on Day 1 prior to the first study vaccination will be considered as baseline.

* A fever can be considered not related to the study product if an alternative etiology can be documented.

DMID/NIAID/NIH

CONFIDENTIAL

DMID Protocol 15-0108	Version 2.0
Phase I Study of HEV-239	08 FEB 2019

† Subjects must not eat or drink anything hot or cold, or smoke within 10 minutes prior to taking oral temperature.

Any symptoms still present at the D8 visit after each vaccination will continue to be followed by subject until symptom resolution. Subjects will also be asked to call the site if they experience any severe symptoms other than what's listed on the e-Memory aid, if they have any severe symptoms that prevents daily activity or any other symptoms and health complaints, even if they are not listed on the e-Memory aid. Sites will review the concomitant medications with the subject at subsequent clinic visits. The subject's input into the electronic data capture system will be reviewed with the subject at subsequent clinic visits.

Subjects will be instructed on how to record daily temperature using a thermometer provided for home use. Subjects should record the oral temperature in the evening post vaccination, and then daily through D8 after each vaccination. Temperature should be measured at approximately the same time each day. If more than one measurement is made on any given day, the highest temperature will be recorded. This information will be reviewed by study staff during follow-up subject contacts.

The site PI/study staff will also assess the vaccination site and measure edema and erythema at the visits post vaccination. Vital sign measurements will be performed at the time points indicated in the **Section 6**. Blood pressure and heart rate measurements should be preceded by at least 5 minutes of rest and in a quiet setting without distractions (e.g., television, cell phones). Confirmatory vital sign measurements can be performed if inconsistent with a prior measurement. A symptom-directed examination will be performed as indicated by the investigator based on any clinically relevant issues, clinically relevant symptoms and medical history. The symptom-directed PE may be repeated if deemed necessary by the investigator. PEs will be performed by a study clinician licensed to make medical diagnoses and listed on the FDA Form 1572 as the site principal investigator or sub-investigator.

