7.1.5 Assessment of Concomitant Medications/Treatments other than Study Product

Medications history (concomitant medications) will include a review of all current medications and medications taken within 30 days prior to signing the informed consent form through Day 57, or Day 29 for those who only receive one dose of study vaccine, or early termination (if prior to Day 29 after any study vaccine dose), whichever occurs first. Concomitant medications will also include all current medications and medications taken within 30 days prior to Vaccine Dose 3 (Day 180) through Day 208. Concomitant therapies outside these times should only be recorded if administered in conjunction with SAEs. Prescription and over-the-counter drugs and vaccines will be included as well as vitamins, herbals, and supplements. Assessment of eligibility will also include a review of all permitted and prohibited medications per the Subject Inclusion and Exclusion Criteria (see Section 5.1.1 and 5.1.2).

Medications that might interfere with the evaluation of the investigational product should not be used unless necessary. Medications in this category include, but are not limited to, glucocorticoids (i.e., oral, parenteral and high-dose inhaled steroids), and immunosuppressive or cytotoxic drugs. Analgesics and antipyretics should be avoided for the 24 hours following study injection, unless necessary.

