10.5.2 Safety Data

Safety data will be summarized for the Safety Analysis Population. Subjects receiving a vaccination according to a study arm other than the study arm to which they were randomized, will be analyzed according to the vaccination they actually received. Solicited AEs will be summarized by severity for each day after each study vaccination for Days 1-8 after each study vaccination. The number, percentage (observed rate), and exact two-sided 95% CI for subjects reporting each solicited AE within 8 days following vaccination will be summarized. In addition, maximum severity for each solicited AE will be determined for each subject and reported by study arm and the resulting number and percentage of subjects will be summarized by severity grade (none, mild, moderate, severe). Summaries of solicited AEs will be presented separately by study arm for each study vaccination as well as overall study vaccinations.

All AEs will be coded by Medical Dictionary for Regulatory Activities (MedDRA®) for preferred term and system organ class (SOC). The final clinical study report will include a summary of all SAEs as well as a summary of all SAEs by relatedness to study product. The number of SAEs considered related to study vaccination are likely to be small in this trial and will be reported by detailed listings showing the event description, MedDRA® preferred term and SOC, relevant dates (study vaccinations and AEs), severity, relatedness, and outcome for each event. Non-serious unsolicited vaccine-related AEs will be summarized as number and percentage of subjects reporting at least one event in each MedDRA® preferred term and SOC, cross tabulated by severity and relationship to study product. Additionally, the proportion of subjects and exact 95% confidence intervals of AEs by study arm for each study vaccination as well as overall study vaccinations and by MedDRA® categories will be calculated.

The number and percentage (observed rate) of subjects that withdrew or discontinued their vaccination series will be tabulated for each study arm.

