9.3.1. Solicited Events and Symptoms

Systemic solicited adverse events were collected pre-vaccination, and systemic and local solicited adverse events were collected 30 minutes post-vaccination and then daily for 7 days after each vaccination and graded on a scale of 0 (absent), 1 (mild), 2 (moderate) and 3 (severe). The grading scales are presented in Table 4 and Table 5. Systemic events include: arthralgia, fever, feverishness, fatigue, headache, malaise, myalgia, nausea, and vomiting. Local events include: ecchymosis severity and measurement, erythema measurement, induration/swelling severity and measurement, pain, pruritus, and tenderness.

The proportion of subjects reporting at least one solicited adverse event will be summarized for each solicited adverse event, any systemic symptom, any local symptom, and any symptoms. The 95% confidence interval (CI) calculated using Clopper-Pearson methodology from a binomial distribution (SAS Proc Freq with a binomial option) will be presented (Table 27).

For each systemic and local event, any systemic event, any local event, and any solicited event, the maximum severity over 7 days after each vaccination will be summarized for the Safety population. The number and percentage of subjects reporting each event will be summarized by the maximum severity and treatment group, separately for each vaccination and over all vaccinations. For each event the denominator is the number of subjects with non-missing data for the specific event (Table 28).

The number of subjects reporting a solicited adverse event will be summarized for each day post vaccination for each vaccination and for all vaccinations combined both in a summary table (Table 29, Table 30, Table 31, Table 32, Table 33, Table 34, Table 35, and Table 36) and graphically in a bar chart (Figure 11, Figure 12, Figure 13, Figure 14, Figure 15, Figure 16, Figure 17, and Figure 18). A comparison of the event rate for each treatment group between vaccination 1 and vaccination 3 will be presented (Table 37). The duration of solicited adverse events will be summarized by dose number and treatment group (Table 38).

Solicited adverse events by subject will be presented in Listing 8 and Listing 9.

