12.2.2 Displays of Adverse Events

Table 4: Solicited Adverse Event Grading Scale – Local (Injection Site) Reactogenicity Grading

Local (Injection Site) Reaction	Mild (Grade 1)	Moderate (Grade 2)	Severe (Grade 3)
Pain – experienced without touching the injection site (spontaneous discomfort)	No pain medication or it requires use of a non-narcotic pain reliever ≤24hours OR does not interfere with activity	Repeated use of non-narcotic pain reliever >24 hours OR interferes with activity	Any use of narcotic pain reliever OR prevents daily activity
Tenderness – hurts only when injection site is touched or the arm is moved	Discomfort only to touch	Discomfort with movement	Significant discomfort at rest
Pruritus (Itching)	Does not interfere with daily activity	Interferes with daily activity	Prevents daily activity
Ecchymosis (Bruising) Severity ^a	Does not interfere with daily activity	Interferes with daily activity	Prevents daily activity
Induration (Hardness)/Swelling Severity ^a	Does not interfere with daily activity	Interferes with daily activity	Prevents daily activity
Ecchymosis (Bruising) Measurement ^b	25mm – 50mm	51 mm – 100mm	>100 mm
Erythema (Redness) Measurement ^b	25 mm – 50 mm	51 mm – 100 mm	>100 mm
Induration (Hardness)/Swelling Measurement ^b	25 mm – 50 mm	51 mm – 100 mm OR interferes with activity	>100 mm OR prevents daily activity

^a Will also be measured in mm but size will not be used as halting criteria.

^b Will not be used as halting criteria.

Systemic	Mild (Grade 1)	Moderate (Grade 2)	Severe (Grade 3)
Feverishness (Chills/Shivering/Sweating)	No interference with daily activity	Some interference with daily activity	Significant interference, prevents daily activity
Fatigue (Tiredness)	No interference with daily activity	Some interference with daily activity	Significant interference, prevents daily activity
Malaise (General Unwell Feeling)	No interference with daily activity	Some interference with daily activity	Significant interference, prevents daily activity
Myalgia (Body Aches/Muscular Pain) ^a	No interference with daily activity	Some interference with daily activity	Significant interference, prevents daily activity
Arthralgia (Joint Pain) ^a	No interference with daily activity	Some interference with daily activity	Significant interference, prevents daily activity

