Headache	No interference with daily activity	Repeated use of non-narcotic pain reliever >24 hours OR some interference with activity	Significant; any use of narcotic pain reliever OR prevents daily activity OR requires triptans
Nausea	No interference with daily activity	Some interference with daily activity	Significant interference, prevents daily activity
Vomiting	No interference with activity or 1-2 episodes/24 hours	Some interference with activity or >2 episodes/24 hours	Prevents daily activity or requires IV hydration
Fever ^b – oral	38.0°C – 38.4°C 100.4°F – 101.1°F	38.5°C – 38.9°C 101.2°F – 102.0°F	>38.9°C >102.0°F

Solicited Adverse Event Grading Scale – Systemic Reactogenicity Grading Table 5:

^a Not at injection site. ^b A fever can be considered not related to the study product if an alternative etiology can be documented

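### The Grade 1 criteria for injection-site pain overlap Grades 2 and 3, and neither document says which grade to record when one state meets two

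*Protocol*

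**What the plan says.** Protocol 8.1.2, Table 3, grades spontaneous injection-site pain as follows:

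- Grade 1: "No pain medication or it requires use of a non- narcotic pain reliever ≤24hours OR does not interfere with activity"
- Grade 2: "Repeated use of non- narcotic pain reliever >24 hours OR interferes with activity"
- Grade 3: "Any use of narcotic pain reliever OR prevents daily activity"

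SAP Table 4 carries the same Grade 1 cell: "No pain medication or it requires use of a non-narcotic pain reliever ≤24hours OR does not interfere with activity".

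In the systemic scale (Table 5 in both documents), Grade 1 headache requires only that daily activity is unaffected, while Grade 2 is "Repeated use of non-narcotic pain reliever >24 hours OR some interference with activity". Grade 3 headache is also met by narcotic or triptan use. Vomiting is graded on activity or on the number of episodes, again joined by *or*.

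Two passages mention a maximum. Protocol 10.5.2 says "maximum severity for each solicited AE will be determined for each subject", and SAP 9.3.1 says "the maximum severity over 7 days after each vaccination will be summarized for the Safety population".

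**The concern.** A severity scale should give each clinical state one grade. Here a subject in severe pain who takes nothing for it satisfies the mildest definition and the most severe one at the same time. Subjects are trained to grade their own reactions in the e-Memory aid (Protocol 6.2), so they apply this wording directly.

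Four things depend on the grade recorded:

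- the severity summaries in SAP Tables 28 to 36;
- the relatedness assessment, which Protocol 8.2 waives for Grade 1 and 2 solicited events;
- the real-time alert for possible Grade 3 entries (Protocol 11);
- the halting criteria for persistent Grade 3 injection-site events (Protocol 8.6.1 and 8.6.2; the study-level rule is also in SAP 6.6). The exemption there for size in millimetres does not cover pain.

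Pain is the local reaction where this matters most: it was the commonest one in the phase 3 trial, at 10.3% versus 5.5% (Protocol 2.3.1).

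**Working it through.** The plan states no figure on this point, so there is nothing to reproduce. The check is a listing of cases.

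**Inputs.** The three pain cells of Protocol Table 3; four levels of analgesic use; three levels of activity (unaffected, interferes, prevents). That gives 4 × 3 = 12 states.

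**Rules, read as written.**

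- Grade 1: no medication, or a non-narcotic for at most 24 hours, or activity unaffected.
- Grade 2: a non-narcotic for more than 24 hours, or interferes.
- Grade 3: a narcotic, or prevents.

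| Analgesic | Unaffected | Interferes | Prevents |
|---|---|---|---|
| None | 1 | 1 and 2 | 1 and 3 |
| Non-narcotic, ≤24 h | 1 | 1 and 2 | 1 and 3 |
| Non-narcotic, >24 h | 1 and 2 | 2 | 2 and 3 |
| Narcotic | 1 and 3 | 2 and 3 | 3 |

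**Result.** Three states meet Grades 1 and 2, three meet Grades 1 and 3, and two meet Grades 2 and 3: 3 + 3 + 2 = 8 of 12. Interference and prevention are treated here as separate levels. If prevention also counts as interference, the narcotic/prevents state becomes Grades 2 and 3, and the total is 8 + 1 = 9 of 12.

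**Effect of two possible repairs.** If the Grade 1 elements were read jointly (as an illustration only), the overlaps would fall to 2 of 12, both between Grades 2 and 3. A rule that the highest grade met is recorded leaves none.

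**Headache and vomiting.** A headache treated with a non-narcotic for more than 24 hours, with activity unaffected, is Grades 1 and 2. One or two vomiting episodes that prevent activity are Grades 1 and 3.

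**Is there a tie-break?**

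- The maximum in Protocol 10.5.2 and SAP 9.3.1, and in the note to the SAP daily severity tables, is taken over grades already recorded. It does not choose between criteria met by one state.
- The general mild/moderate/severe guide in Protocol 8.1.1.1 covers only events outside the protocol's own scales.
- Protocol 8.1.2 does give recording rules elsewhere: the highest temperature of the day is kept, and bruising and swelling are graded on both the symptom and size scales. Pain has no equivalent.

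**Where the grade counts.** Among 20 vaccinees, one regraded subject moves a severity percentage by 1/20 = 5 points. The study-level halting rule needs two subjects with the same persistent Grade 3 injection-site event; the individual rule turns on one subject.

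**The case against.** The best defence is that the effect will be small in practice. Site staff review the e-Memory entries with the subject at the Day 4 call and Day 8 visit, and Protocol 11 makes the clinically reviewed data the source for the endpoints. Subjects are told to call about severe symptoms that prevent daily activity (Protocol 8.1.2), which is itself a cue that such pain is not mild. Many assessors would record the higher grade unprompted. Protocol 8.6.2 also lets the investigator suspend vaccination or ask for an ad hoc committee meeting.

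Grade 3 local reactions are also likely to be few. Phase II saw them in only two dose groups, at 1.6% and 1.7% per dose (Protocol 2.3.1). Assuming those rates applied to 20 × 3 = 60 vaccine doses, the expected number is 60 × 0.016 = 0.96 to 60 × 0.017 = 1.02, for local reactions of every kind.

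Much of this stands, and it rules out three stronger readings that a reader might infer:

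- *That the primary endpoint is affected.* It counts solicited events (Protocol 3.3.1, SAP 3.2.1). Pain counts whatever its grade, so SAP Table 27 is unchanged.
- *That the protocol steers subjects into Grade 1 by discouraging analgesics.* Protocol 7.1.5 says only "Analgesics and antipyretics should be avoided for the 24 hours following study injection, unless necessary". The halting criteria need 3 or more days, well beyond that request, and the overlap exists without it. Neither document gives the rate of analgesic use or the day of peak pain.
- *That a halt would be missed.* This needs a literal low grade, persistence, no correction at review and, for the study-level rule, a second subject with the same event. The documents allow this but do not show it to be likely.

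The defence does not remove the defect. Reviewing staff use the same table, under which a Grade 1 entry for untreated pain that prevents activity is not an error. The habit of taking the higher grade is not written down.

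**Conclusion.** The point holds as a defect in the grading rule. As written, 8 of 12 pain states carry more than one grade, 3 of them both Grade 1 and Grade 3, and nothing in either document resolves the conflict. The severity summaries, the relatedness step, the Grade 3 alert and the injection-site halting criteria are exposed; the count of solicited events is not.

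How often misgrading would occur cannot be estimated: the documents give no joint distribution of analgesic use and activity limitation. The conclusion rests on a literal reading of the table and on the e-Memory aid and its instructions following that wording. Those materials and the manual of procedures were not available; if they already impose a highest-grade rule, what remains is to write that rule into the protocol and SAP.

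**What to change.** Three changes:

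1. Reconcile the Grade 1 pain wording in Protocol Table 3 and SAP Table 4 with the Grade 2 and Grade 3 cells. The sponsor should settle the clinical wording.
2. Add one recording rule under the local and systemic scales in both documents: if the criteria for more than one grade are met, the highest grade is recorded. This is the essential change, since rewording Grade 1 alone can leave overlaps between Grades 2 and 3. It also settles headache and vomiting.
3. Confirm that the e-Memory aid and its instructions apply the same rule, so that the alert and the eCRF agree.

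The cost is a few words in each document and one check of the e-Memory aid. The downside is that some events will be reported at a higher grade. No halting rule or clinical threshold needs to change.
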